### Follow-up Visit (Week 28)

All subjects will have a follow-up visit 4 weeks after the last dose of Basaglar. Assessments at this visit will be done as detailed in Section 2. Subjects who withdraw from the study will also have assessments done similar to those at the follow-up visit.

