### 9.1. Efficacy and Safety Assessments

#### 9.1.1. Primary Safety Assessments

##### Hypoglycemia

Information on treatment-emergent hypoglycemic events starting from Visit 2 until the last study visit (Visit 9 or early termination [ET] visit) will be collected. Subjects will be trained about signs and symptoms of hypoglycemia. Subjects will be trained to check and record their blood glucose levels if they experience symptoms suggestive of hypoglycemia. For each hypoglycemic event, subjects should record the following data in the study diaries provided by the sponsor via the investigator:

- blood glucose levels
- associated symptoms
- treatment, and
- other pertinent information.

A hypoglycemic event is defined as any time a subject feels that he or she is experiencing a sign or symptom that is associated with hypoglycemia or has a FBG level of  $\leq 54$  mg/dL (3.0 mmol/L), even if it was not associated with signs, symptoms, or treatment consistent with current guidelines.

**Severe hypoglycemia:** An event requiring assistance of another person to actively administer carbohydrates or glucagon or taking other corrective actions. Blood glucose concentrations may not be available during an event, but neurologic recovery following the return of blood glucose to normal levels is considered sufficient evidence that the event was induced by a low blood glucose concentration.

**Nocturnal hypoglycemia:** Any total hypoglycemic event that occurs after bedtime and prior to the first meal in the morning.

**Documented symptomatic hypoglycemia:** An event during which typical symptoms of hypoglycemia are accompanied by a blood glucose level of  $\leq 54$  mg/dL ( $\leq 3.0$  mmol/L) as confirmed by blood glucose measurement.

**Asymptomatic hypoglycemia:** Any event not accompanied by typical symptoms of hypoglycemia but a measured a blood glucose level of  $\leq 54$  mg/dL ( $\leq 3.0$  mmol/L) was observed.

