6.2 Full Analysis Set (FAS) / Safety Analysis Set (SAF)

FAS and SAF are identical to each other as this is single arm trial and no randomization occurs. So, we will indicate this population as FAS for analysis purpose.

This population will include all enrolled participants who take at least 1 dose of study treatment.

 "Y" for subjects who received at least one dose of the investigational product (IMP). Else set to "N".

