6.3 Per-Protocol Analysis Set (PPS)

This analysis population will include all FAS subjects, who also meet the following criteria:

- a) Have no violations of inclusion/exclusion criteria
- b) Have not discontinued from the study prior to 24 weeks
- c) Have not been off study medication for more than 14 consecutive days during the treatment period
- d) Have not received chronic (lasting longer than 14 consecutive days) systemic glucocorticoid therapy (excluding topical, intra-articular, intra-ocular, and inhaled preparations)
 - Set to 'Y' if
 1. For all FAS subjects = "Y" and

- Date of completion/discontinuation is not less than date of visit 8 (week 24)
- 3. within a subject there is no DV.DVCAT = "MAJOR"

CONFIDENTIAL CS.BS.01.00 TPL-1.0: Statistical Analysis Plan Template

Page 19 of 85

7. General considerations

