8.2 Missing data

- Vital Signs: we will use the last observation carry forward (LOCF) method for the missing values.
- 2) Actual and Change from Baseline HbA1c: For subjects requiring rescue medication, HbA1c values recorded after the first administration of rescue medication will not be considered for analysis, and these values will be considered as missing. In addition, for the actual value and change from baseline, a descriptive analysis using LOCF will be performed, using the baseline or 12-week value, if the 24-week value is missing or occurred after use of rescue medication.
- 3) Subjects Reaching HbA1c Targets (≤6.5% and <7%) at Week 24: The HbA1c values used to calculate this binary variable will be the LOCF value, that is, in case the Week 24 value is missing, the Week 12 value will be used. The denominator will be the total FAS population. Subject with missing HbA1c data at Week 12 and Week 24 will be considered as not having reached the target.

For other efficacy parameters 7-point SMBG levels (mg/dL and mmol/L), body mass index (kg/m²), body weight (kg), basal insulin dose (U/day and U/kg/day) we will apply the LOCF method for missing data.

4) ITSQ score: If an item score is missing for a subject and ≤20% of the items within the domain (or overall) are missing for that subject, then the mean of the items scores in the domain (or overall) will be imputed for the missing item score(s). If there are >20% missing items, the individual subject domain (or overall) score will be set to missing. that is here we will use the mean imputation method.

Page 25 of 85

Change at Week 24 from Week 4 for ITSQ score (Transformed overall and domain scores): we will use the last observation carry forward (LOCF) method for the missing values.

5) Laboratory data: we will use the last observation carry forward (LOCF) method for the missing values.

For all other cases the missing data will not be imputed for this trial.

9. Output presentations

This is single arm study; we are not doing any stratification we will present the summary table for single treatment group i.e. Basaglar.

The Section 23, Appendix 1 describe the format and content for presentation of tables, listings and figures (TLFs).

All percentages (%) for a specific summary are calculated using the total number of participants included in the relevant analysis population as the denominator, unless otherwise specified.

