- Were signs/symptoms of hypoglycemia present, other than the blood glucose reading? (In eCRF "Hypoglycemia Events" form)
- Hypoglycemic event start date
- Date of Visit 2 (Week 0)
- Date of Visit 8 (Week 24)

Derivation:

- Hypoglycemic event start date ≥ Date of Visit 2 (Week 0) and Hypoglycemic event start date ≤ Date of Visit 8 (Week 24) for accessing the hypoglycemic events from Day 0 to week 24.
- "Symptomatic Hypoglycaemic events" if, the question "What was the blood glucose level (mg/dL) prior to treating the event" result is less or equal to 54 mg/dL and the question "Were signs/symptoms of hypoglycemia present, other than the blood glucose reading" is answered as "YES".
- "Asymptomatic Hypoglycaemic events" if, the question "What was the blood glucose level (mg/dL) prior to treating the event" result is less or equal to 54 mg/dL and the question "Were signs/symptoms of hypoglycemia present, other than the blood glucose reading" is answered as "NO" or "UNKNOWN.

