19.2 Analyses

19.2.1 Primary analysis

Population: FAS and PPS

Stratification: Table: NA

Page 54 of 85

Listing: By subject

Statistics:

The total hypoglycaemic event will be analysed as number and percentage (n and %) of subjects experiencing at least 1 event from Day 0 to Week 24.

The estimate and 95% confidence interval will be presented by using exact binomial method (Clopper-Pearson method) for single proportions for the incidence of total hypoglycaemic events from Day 0 to Week 24.

The listing will be presented for all the hypoglycaemic events.

20. Secondary efficacy assessments

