20.1.3 Incidence and rates per 30 days and per subject-year of nocturnal, severe, documented symptomatic and asymptomatic hypoglycemic events

Variables:

Page 57 of 85

- What was the blood glucose level (mg/dL) prior to treating the event? (In eCRF "Hypoglycemia Events" form).
- Were signs/symptoms of hypoglycemia present, other than the blood glucose reading? (In eCRF "Hypoglycemia Events" form).
- When did the hypoglycemic event occur? (In eCRF "Hypoglycemia Events" form).
- Did the subject experience a severe hypoglycemic episode with neurological (cognitive) impairment requiring assistance from another person? (In eCRF "Hypoglycemia Events" form).
- Hypoglycemic event start date
- Date of Visit 2 (Week 0)
- Date of Visit 8 (Week 24)
- Date of Visit 9 (Week 28)
- Date of first IMP dose administration (In eCRF "Exposure" form)
 Date of last IMP administration (In eCRF "End of Study" form)

Derivation:

- Hypoglycemic event start date ≥ Date of Visit 2 (Week 0) and Hypoglycemic event start date ≤ Date of Visit 8 (Week 24) for accessing hypoglycemic events from Day 0 to week 24 (for the incidence and rate of hypoglycemic events endpoint).
- Hypoglycemic event start date ≥ Date of Visit 2 (Week 0) and Hypoglycemic event start date ≤ Date of Visit 9 (Week 28) for accessing hypoglycemic events from Day 0 to week 28 (only for the rate of hypoglycemic events endpoints).
- If in eCRF "Hypoglycemia Events" form the question if, the question "What was the blood glucose level (mg/dL) prior to treating the event hypoglycaemic event occur" result is less or equal to 54 mg/dL and the question "when did the hypoglycemic event occur" is answered as "BETWEEN BEDTIME AND PRIOR TO FIRST MEAL IN MORNING" then we will consider it as nocturnal hypoglycemia.
- If in eCRF "Hypoglycemia Events" form the question "What was the blood glucose level (mg/dL) prior to treating the event hypoglycaemic event occur" result is less or equal to 54 mg/dL and the question "Did the subject experience

a severe hypoglycemic episode with neurological (cognitive) impairment requiring assistance from another person" is answered as "YES" then we will consider this as severe hypoglycemia.

• For Documented symptomatic hypoglycemia and documented asymptomatic hypoglycemia see the derivation mentioned in section 19.1.1.

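### The primary incidence window closes at each subject's Visit 8 date with no substitute, so read literally it drops the recorded hypoglycaemic events of FAS subjects who have no Visit 8

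*SAP*

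**What the plan says.** The dates listed for the primary derivation in SAP 19.1.1 are the event start, Visit 2 and Visit 8. The upper limit is "Hypoglycemic event start date ≤ Date of Visit 8 (Week 24) for accessing the hypoglycemic events from Day 0 to week 24". SAP 20.1.3 uses the same limit for the incidence of the hypoglycaemia subtypes and reserves the longer window, to Visit 9, for the rates.

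SAP 19.2.1 defines the primary result as "number and percentage (n and %) of subjects experiencing at least 1 event from Day 0 to Week 24". The analysis set is the FAS (SAP 6.2): "This population will include all enrolled participants who take at least 1 dose of study treatment". On denominators, SAP 9 says: "All percentages (%) for a specific summary are calculated using the total number of participants included in the relevant analysis population as the denominator".

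Protocol 9.1.1 says that information on treatment-emergent hypoglycaemic events "starting from Visit 2 until the last study visit (Visit 9 or early termination [ET] visit) will be collected". Protocol 5.1.1 adds: "Subjects who withdraw from the study will also have assessments done similar to those at the follow-up visit". In both schedules of activities, early termination shares the Visit 9 column, not the Visit 8 column.

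Nothing elsewhere supplies a Visit 8 date. SAP 8.2 limits imputation to listed items, and these include neither hypoglycaemia nor visit dates. SAP 7.1 announces visit windowing but has no rule that turns an early-termination date into a Visit 8 date.

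**The concern.** A subject who has a qualifying event in Week 6 and leaves in Week 10 has had an event between Day 0 and Week 24, so SAP 19.2.1 counts that subject. SAP 19.1.1 does not, because there is no Visit 8 date for the event to precede. The subject stays in the denominator as a non-event.

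This is the trial's only primary number, and it measures risk. The literal rule can lower it but never raise it. Subjects without a Visit 8 may also include some with events, because Protocol 8.2 lists persistent hypoglycaemia among the grounds for discontinuation.

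Two neighbouring rules depend on the same date:

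- **PPS (SAP 6.3).** Criterion b is meant to remove subjects who leave before 24 weeks. Its operational form compares the completion or discontinuation date with the Visit 8 date, so it is undefined for the very subjects it should exclude.
- **Week 24 rates (SAP 20.1.2, 20.1.3, 20.2.2).** Events are windowed to Visit 8, the text of 20.2.2 speaks of baseline to end of treatment or study, and the model offset runs to the last dose (SAP 12.1). Without a Visit 8 date the number of days in the rate formula is undefined. The direction of any bias in the rates cannot be determined, so no figure is given for them.

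**Working it through.** **What the literal rule does.** SAP 7.6 names SAS. SAS sorts a missing date below every real date, so the test that the event date is no later than the Visit 8 date is false and the event is dropped without warning. In the PPS rule, the test that the discontinuation date is not less than the Visit 8 date is true for the same reason, so an early terminator could pass it unless a major deviation is recorded.

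**Inputs from the documents.** Protocol 5.2 and Table ABEX.3: n = 250; planning incidences 5/46 = 10.9% (11%) and 146/489 = 29.9% (30%); drop-out 20%. SAP 19.2.1: Clopper-Pearson 95% interval.

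**The plan's own figures reproduce.** Half-width = 1.96 × √(p(1−p)/n). For p = 0.11 the SE is 1.98% and the half-width 3.88 points (stated 3.9). For p = 0.30 they are 2.90% and 5.68 points (stated 5.7).

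**Assumptions.** The documents do not give d, the share of the FAS without a Visit 8. The 20% drop-out refers to study completion, and a subject lost after Visit 8 does have a Visit 8 date, so I take d = 5%, 10% and 20%. I also assume exit times uniform over 24 weeks, a constant hazard, and the same hazard in dropouts as in others.

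**Formulas.** Let p be the 24-week risk and λ = −ln(1−p).

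- As written: (1−d)p.
- With events up to exit counted: (1−d)p + d·b, where b = 1 − p/λ is the chance of an event before a uniform exit time.
- p = 0.11: λ = 0.1165, b = 0.0561. p = 0.30: λ = 0.3567, b = 0.1589.
- Loss = d·b.

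| p | d | As written | Events to exit counted | Loss, points | Loss, subjects of 250 | CI coverage, as written | CI coverage, corrected |
|---|---|---|---|---|---|---|---|
| 11% | 5% | 10.45% | 10.73% | 0.28 | 0.7 | 95.6% | 95.9% |
| 11% | 10% | 9.90% | 10.46% | 0.56 | 1.4 | 95.7% | 96.2% |
| 11% | 20% | 8.80% | 9.92% | 1.12 | 2.8 | 92.8% | 95.7% |
| 30% | 5% | 28.50% | 29.29% | 0.79 | 2.0 | 95.6% | 96.3% |
| 30% | 10% | 27.00% | 28.59% | 1.59 | 4.0 | 92.1% | 95.8% |
| 30% | 20% | 24.00% | 27.18% | 3.18 | 7.9 | 83.1% | 96.1% |

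Coverage is the exact binomial probability that the Clopper-Pearson interval contains the incidence with events to exit counted. The chance that the whole interval lies below that value, as written, is 3.2%, 3.5% and 6.8% in the 11% case and 3.5%, 7.5% and 16.8% in the 30% case.

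**Sensitivity.** If subjects without a Visit 8 instead had the full planning incidence recorded before they left, the loss would be d·p. At d = 20% that is 0.20 × 11 = 2.2 points (22/250 against 27.5/250) or 0.20 × 30 = 6.0 points (60/250 against 75/250). At d = 5% it is 0.55 or 1.5 points. The loss is zero only if no subject without a Visit 8 had a recorded event.

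**The case against.** The strongest reply is that this is an omission rather than an error. The derivation line states its purpose, to find events from Day 0 to Week 24, and SAP 19.2.1 repeats that period. A sensible programmer would read Visit 8 as end of treatment, and the loss would vanish. It is true that the intent is clear and that the bias arises only if the rule is coded as written. But the written rule gives a different answer from the measure it serves, and the choice that avoids this is nowhere stated.

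Other points have partial force:

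- **Events are not hidden.** All are listed, and the rates to Week 28 may capture early terminators if the ET date fills the Visit 9 field. Neither repairs the primary incidence.
- **The PPS has a safeguard.** SAP 6 requires agreement on populations before hard lock, with a sponsor list of exclusions. This makes wrong admission to the PPS less likely but leaves the primary window as it is.
- **The corrected incidence is still cut short by drop-out.** At d = 20% it is 9.92% and 27.18%, against 24-week risks of 11% and 30%. The interval then covers those risks with probability 94.1% and 85.4%. This is ordinary censoring, which the fix does not claim to remove. The coverage figures above concern recorded events only.
- **The size is uncertain.** The 11% case comes from the insulin-naïve Indian subgroup, the closest match to this trial, and it shows no undercoverage at 5% or 10%.
- **There is no comparator or threshold**, so no decision changes.

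**Conclusion.** The concern holds. As written, SAP 19.1.1 excludes recorded events of FAS subjects who have no Visit 8 while keeping those subjects in the denominator, and this conflicts with SAP 19.2.1. Under the stated assumptions the understatement ranges from 0.3 to 1.1 points in the 11% case and from 0.8 to 3.2 points in the 30% case as the share without a Visit 8 goes from 5% to 20%. Interval coverage falls below 95% only in the 30% case from 10% upward and in the 11% case at 20%.

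Confidence is high that the fallback is missing and that the literal effect is downward. The size is conditional on a share the documents do not give, on risk among dropouts, and on how the rule is programmed. It should be fixed before the analysis is programmed, because a primary safety result should not rest on an unstated choice.

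**What to change.** - **SAP 19.1.1 and the Day 0 to Week 24 windows in 20.1.2 and 20.1.3:** close the window at the Visit 8 date. If Visit 8 did not occur, close it at the earlier of the ET/last-contact date and Day 175 (Day 168 + 7, on the day scale of SAP Table 7.1, where Visit 2 is day 0). Count all events of all FAS subjects up to that date.
- **Rates:** state one period and use it for the event count, the days in the rate formula and the model offset, and reconcile it with the period named in 20.2.2. The offset now runs to the last dose, so changing only the event window would leave the two unmatched.
- **SAP 6.3:** replace the Visit 8 comparison with one that is defined when Visit 8 is missing.
- **Disposition table:** report the number of FAS subjects without a Visit 8.

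The cost is a few derivation lines in 19.1.1, 20.1.2, 20.1.3 and 6.3, a matching offset definition and one extra count. No new data are needed. The reported incidence may be slightly higher.

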19.2 Analyses

19.2.1 Primary analysis

Population: FAS and PPS

Stratification: Table: NA

Page 54 of 85

Listing: By subject

Statistics:

The total hypoglycaemic event will be analysed as number and percentage (n and %) of subjects experiencing at least 1 event from Day 0 to Week 24.

The estimate and 95% confidence interval will be presented by using exact binomial method (Clopper-Pearson method) for single proportions for the incidence of total hypoglycaemic events from Day 0 to Week 24.

The listing will be presented for all the hypoglycaemic events.

20. Secondary efficacy assessments

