### **5.2. Number of Participants**

Assuming a 15% screen failure rate, approximately 295 subjects will be screened, so that 250 subjects can be enrolled. Assuming a drop-out rate of 20%, the target is to have a minimum of 200 subjects completing the present study.

In the India subpopulation of ELEMENT 5 study, 5 of the 46 insulin-naïve subjects experienced at least 1 hypoglycemic event (total hypoglycemia incidence with glucose levels  $\leq 54$  mg/dL [3.0 mmol/L]) during the overall study period. When considering the total ELEMENT 5 population, 146 out of 489 subjects (30%) experienced at least 1 hypoglycemic event during the overall study period. Based on these estimates, the precision with 250 and 200 subjects would be as outlined in [Table ABEX.3](#) (95% confidence interval for proportion shown based on normality assumption).

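### The primary 24-week incidence counts subjects who leave early without an event as event-free to Week 24, so under the planned 20% drop-out it tends to understate the 24-week risk

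*SAP*

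**What the plan says.** SAP 19.2.1 has the primary endpoint "analysed as number and percentage (n and %) of subjects experiencing at least 1 event from Day 0 to Week 24". For precision, "The estimate and 95% confidence interval will be presented by using exact binomial method (Clopper-Pearson method) for single proportions". Protocol 10.3.2.1 uses the same crude proportion with a normal-approximation interval.

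The denominator comes from SAP section 9: "All percentages (%) for a specific summary are calculated using the total number of participants included in the relevant analysis population as the denominator". SAP 6.2 defines the FAS: "This population will include all enrolled participants who take at least 1 dose of study treatment". SAP 8.2 lists the endpoints that have a missing-data rule. Hypoglycaemia is not among them, and the section closes with: "For all other cases the missing data will not be imputed for this trial".

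On follow-up, protocol 5.2 says: "Assuming a drop-out rate of 20%, the target is to have a minimum of 200 subjects completing the present study". Protocol 9.1.1 collects hypoglycaemic events up to Visit 9 or the early termination visit.

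The primary analysis is repeated in the PPS, which excludes anyone who discontinued before 24 weeks (SAP 6.3). Exposure is allowed for only in the secondary event rates, through an offset in the negative binomial model (SAP 20.1.2 and 20.2.2). Neither document plans a time-to-first-event or cumulative-incidence analysis.

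**The concern.** The endpoint is worded as incidence at Week 24, which reads as the risk of at least one event over 24 weeks of treatment. The estimator takes everyone dosed as the denominator, but a subject who leaves at Week 6 can contribute an event only up to Week 6. If that subject had none, the remaining 18 weeks are in effect scored as free of hypoglycaemia.

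For a safety endpoint this error is in the reassuring direction, and a larger sample does not reduce it. The exact binomial interval treats every subject as fully observed, so it is centred too low for the 24-week risk. The plan is more cautious elsewhere: for the HbA1c targets, a subject with both post-baseline values missing counts as not having reached the target.

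**Working it through.** **Inputs from the documents.** 250 enrolled, 20% drop-out, 200 completing (protocol 5.2). Planning incidences: 5/46 = 10.9%, used as 11% (insulin-naive Indian subjects in ELEMENT 5), and 146/489 = 29.9%, used as 30% (total ELEMENT 5 population). Two-sided 95% Clopper-Pearson interval (SAP 19.2.1).

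**The plan's own figures reproduce.** 200/(1 − 0.20) = 250, and 250/(1 − 0.15) = 294.1, against about 295 screened. The half-width 1.96·√(p(1−p)/n) gives 3.88 and 5.68 points at n = 250, and 4.34 and 6.35 points at n = 200. Table ABEX.3 has 3.9, 5.7, 4.3 and 6.4. That table takes all 250 (or 200) subjects as fully observed.

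**Assumptions, because the documents give no time pattern.** Drop-out is independent of hypoglycaemia and the hazard of a first event is constant. Leavers' events before departure are counted.

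**Formula.** Let 24 weeks be one unit of time, p the true 24-week risk, d = 0.20 and λ = −ln(1 − p). The expected crude proportion is (1 − d)·p + d·E[1 − exp(−λC)], where C is the drop-out time. For C uniform on (0, b), the expectation is 1 − (1 − exp(−λb))/(λb).

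- p = 0.30, λ = 0.3567, b = 1: expectation 1 − 0.30/0.3567 = 0.159; crude = 0.240 + 0.2 × 0.159 = 0.272.
- p = 0.30, b = 0.5: expectation 0.084; crude = 0.240 + 0.017 = 0.257.
- p = 0.11, λ = 0.1165, b = 1: expectation 0.056; crude = 0.088 + 0.011 = 0.099.
- p = 0.11, b = 0.5: expectation 0.029; crude = 0.088 + 0.006 = 0.094.

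Coverage is the exact binomial sum at n = 250: the probability that the Clopper-Pearson interval contains p when the count has the crude proportion as its mean.

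| Drop-out (20%) | True 11%: mean, coverage | True 30%: mean, coverage |
|---|---|---|
| None | 11.0%, 96.7% | 30.0%, 95.5% |
| Last 4 weeks only | 10.8%, 96.6% | 29.6%, 95.4% |
| Uniform over 24 weeks | 9.9%, 94.1% | 27.2%, 85.4% |
| Uniform over first 12 weeks | 9.4%, 90.4% | 25.7%, 70.1% |
| First 4 weeks only | 9.0%, 86.6% | 24.6%, 55.1% |

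At 30% with uniform drop-out, the upper limit falls below the true risk in 14.5% of trials and the lower limit lies above it in 0.1%.

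**Other patterns.** If two thirds of the cumulative hazard falls before Week 12, uniform drop-out gives biases of −0.9 points (11%) and −2.3 points (30%). Front-loading of detected events is plausible, because daily fasting glucose is mandatory only to Week 12. With constant hazard and 10% uniform drop-out, the biases are −0.5 and −1.4 points, with coverage 96.1% and 93.3%. Over all the 20% patterns tried (front-loaded, constant and back-loaded hazards), bias ran from −0.1 to −2.1 points at 11% and from −0.3 to −5.6 points at 30%. It was never upward.

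**Kaplan-Meier under the same conditions.** In 10,000 simulated trials per scenario, 1 minus Kaplan-Meier with log-log limits averaged 11.0% and 30.0%, with coverage 94.7% to 95.3%. Mean half-widths were 4.0 to 4.4 points (11%) and 5.7 to 6.3 points (30%), close to Table ABEX.3.

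**The case against.** The strongest defence is that protocol 10.3.2.1 defines the analysis operationally, as the percentage with at least one event over the study period, and the crude proportion estimates that without bias. The ELEMENT 5 planning figures have the same form, no test or threshold depends on the result, and exposure-adjusted rates are already secondary. This stands as a reason to keep the crude figure in the table. It does not make that figure an estimate of 24-week risk, which is how a reader will take incidence at Week 24. Neither document states a while-observed estimand.

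The trial population is insulin-naive, so 11% is the closer planning figure. There, evenly spread drop-out costs 1.1 points against a planned half-width of 3.9, and coverage is about 94%. This stands. Also, the 20% refers to completing the study, which includes the Week 28 visit, so anyone lost after Week 24 loses no primary follow-up.

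Kaplan-Meier has its own assumption. Protocol 8.2 allows withdrawal for persistent hypoglycaemia or increased risk of it, so censoring may be informative. Suppose leavers had twice the hazard of others, with an overall risk of 30% and uniform drop-out (an assumption for illustration). Kaplan-Meier would then give about 28.3% and the crude proportion 25.9%: closer, but still low. This stands and calls for a sensitivity analysis.

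Three stronger readings are tempting but not supported:

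- **That all 50 expected leavers are scored event-free.** This would give 0.8 × 30% = 24.0%, or 8.8% for a true 11%. As SAP 19.2.1 describes the estimator, an event before leaving counts; only event-free leavers are affected. The derivation window in SAP 19.1.1 ends at the Visit 8 date, which early leavers lack. That is a separate programming matter.
- **That the PPS repeat fails simply because it conditions on completion.** If drop-out is unrelated to hypoglycaemia, the completers' proportion is unbiased (simulated 11.0% and 30.0%). The PPS is unsafe because that condition may fail, and because it excludes subjects for other reasons, including rescue use (protocol 7.4).
- **That the interval generally misses its 95% level.** This holds near 30% or with early drop-out. It does not hold at 11% with even or late drop-out.

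**Conclusion.** The concern holds in this limited form. As an estimate of 24-week risk, the crude FAS proportion is biased downwards whenever subjects leave before Week 24 independently of risk. At the planned 20% drop-out, with constant hazard and uniform departure, the bias is about 1 point at a true 11%, with little loss of coverage. At a true 30% it is about 3 points, half the planned half-width of 5.7, and coverage falls to about 85%. Earlier departure makes it worse and late departure makes it negligible. The direction is firm under independent drop-out. The size is not, because it rests on assumed timing and on 20% being lost before Week 24. The plan should be changed, because the error favours reassurance on the primary safety endpoint and the dates needed to remove most of it are already captured.

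**What to change.** In SAP 19.2.1 and protocol 10.3.2.1:

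1. In the FAS, report 1 minus the Kaplan-Meier estimate at Week 24 (Day 168 in SAP 7.1), with a log-log 95% interval, as the estimate of 24-week incidence. Time the first event from first dose and censor at the earliest of last dose, discontinuation and Week 24. Give the number at risk at the evaluation day, because Visit 8 has a ±7-day window and some completers will be censored a few days early.
2. Keep n (%) with the exact interval beside it, for comparison with the crude planning figures.
3. Treat death before a first event as a competing event.
4. Add a sensitivity analysis for informative censoring, for example counting withdrawals for hypoglycaemia or hypoglycaemia risk as events. The discontinuation reasons in SAP 10.1 have no hypoglycaemia category, so specify before lock how these withdrawals will be identified.
5. Do the same for the nocturnal, severe, documented symptomatic and asymptomatic subtypes.

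No new data are needed: SAP 10.1, 12.1 and 19.1.1 already use the event start, first dose, last dose and completion or discontinuation dates. The costs are some programming, a slightly wider interval and reliance on independent censoring. Protocol 10.3.1 requires an amendment when a principal feature changes, so the edit to 10.3.2.1 may need one.
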